4.2 Scientific Rationale for Study Design

The retrospective cross-sectional study design was selected because the desire is to examine the pregnancy rates and perception of useability and safety of the Mosie Kit. Since this is a post-market study, the use of an existing group of participants who voluntarily purchased and used the Mosie Kit exists and provides an excellent group of participants to study. The past experiences of these participants will provide valuable information for future participants on the success rate of at-home insemination, information as to the ease of use of the instructions included in the kit, ease of use of the kit, and perceived safety.

The rationale for examining the participants first as a complete cohort and then stratified by type of relationship, infertility source, and age group is that the primary hypotheses relate to overall pregnancy rates using the at-home insemination Mosie Kit and the rate of pregnancy in women without a known fertility cause wanting to get pregnant without intercorse. The type of relationship is also important because a woman in an LGBTQ relationship without fertility issues is more likely to easily get pregnant than a heterosexual female with fertility issues once the semen is deposited at or near the cervix. While there might be LGBTQ women that also have a known cause of fertility, they will be examined by type or relationship as well as by infertility source. Likewise, single women will be categorized by their known infertility source or as not having a known fertility issue. It is important to study the difference between the two groups and explore the impact on the overall pregnancy rate of Mosie Kit users.

Additional hypotheses aim to examine more specifics related to each stratification. For example, age is known to affect fertility rates. Women ages 20-30 are more likely to get pregnant than those in their 40s. The source of infertility may also indicate underlying biological or physical issues that might mediate the pregnancy rates causing different rates of success in each of the groups. All the information obtained through this study will be used to benefit people who are trying to get pregnant and are experiencing infertility issues. Specifically, the study will examine the viability and success rate of at-home insemination.

Another benefit of conducting a retrospective study is being able to examine the natural use of the Mosie Kit. While instructions are provided as to how and when to use the Mosie Kit for insemination, it is known that there will be a variation of use among study participants. This might affect the pregnancy outcome. Therefore, one of the tertiary hypotheses will collect information related to timing and dosing (with dosing being the instance of insemination). This is important because the results will help provide information that will help ensure future studies have clearer instructions and so that all users regardless of study participation optimize the use of the Mosie Kit in order to get pregnant.

4.3 Justification for Intervention

This is a retrospective cross-sectional study of existing users of the Mosie Kit. Participants will be recruited via email. Specifically, it is planned that participants will receive up to 5 email invitations to participate in the study, however more emails might be used to recruit sufficient participants.. The email will direct them to the study survey where they will read the consent form and choose to participate in the study. The email will contain a link to the survey. If they elect to participate, they will complete the study survey and submit it online. Participation consists of completing a 10-20 minute survey. This is a one time survey. Since no identifying information will be collected, there will be no possibility of follow up.

There is no intervention. This study merely looks at the past experience of using the Mosie Kit. It is important to know the success rates of pregnancy with at-home insemination kits, and understand the usability and safety as there are individuals and couples using these types of options on a regular basis as a means to get pregnant. For people who suffer from infertility, having this information will help them choose whether ICI is right for them and whether the Mosie Kit should be chosen for this method. Additionally, since age is a factor in pregnancy success and risks increase with age, there is a need to understand the success of at home ICI so recommendations can be made as to whether to use ICI and how long to use it before seeking other methods of conception. This study aims to address some of these issues.

4.4 End-of-Study Definition

It is expected that the study will be completed within 30 days of the initial email. This will provide participants with an opportunity to find 10-20 minutes to participate in the study during a 30 day window. Participants will receive up to three additional reminder emails at least 7 days apart and one final email 2 days prior to study close. Participants who choose to participate in the study will be considered to have completed the study upon submission of the complete survey. If sufficient participants have not completed the survey, the study timeframe may be expanded at the discretion of the PI.

5 STUDY POPULATION

The study population will consist of all individuals who have purchased the Mosie Kit in the past 2-8 complete months prior to study initiation. All qualifying individuals will receive an invitation to participate. These individuals will typically be of child-bearing age, both females and males, and generally ages ranging 18-50 years old.

It is assumed that purchasing the Mosie Kit means the kit will be used as intended for at-home insemination. One of the inclusion criteria is to have previously used the kit. Therefore, the initial list of study participants will be drawn from people who have placed a purchase order within the prior 8 complete months; complete months are used with the expectation that the Mosie Kit would be used within the month post-purchase. If the study duration is expanded, additional potential participants will be invited who have purchased the kit at least 2 full months prior to being invited to participate in the study.

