1.2 Schema

Following is the flow of this study.

[figure not shown]
Total N: approximately 500. (approximately 4000 invitation emails) Identify all potential participants by obtaining a list of all people who have purchased a Mosie Baby Kit in the 2-8 full months prior to the initiation of the study. No other inclusion/exclusion criteria applies at this point.

Send all participants an initial email requesting their participation in the study. Up to an additional 4 reminder emails will be sent to encourage participation.

TIME POINT 1: Online survey completion.

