2.3.2 Known Potential Benefits

The potential benefit of this study is mostly for people seeking to perform at-home intracervical insemination in the future using the Mosie Kit. Each Mosie Kit provides syringes for two inseminations to occur within a cycle at the cost of about \$89. This is less than 20% of the cost of IUI which can range between \$500-1500/ procedure before labs, ultrasounds, and additional expenses, and around 5% once all costs are added up. The study will provide valuable information to people trying to conceive about the efficiency of using the Mosie Kit for ICI, how that efficiency might compare to the effectiveness of IUI, and how the cost of each compares. This will help the user decide whether the Mosie Kit is the right conception tool for them. The study will also provide valuable information about the safety and usability of the kit. The research will let Mosie know if they have successfully communicated how to use the kit, if the instructions are clear or if any changes are needed, and whether anything else should be considered in future design changes. The study might also provide information on the timing of the insemination that might lead to a positive pregnancy outcome. Additionally, this knowledge might provide Mosie Baby with information to help it position itself better in the market..

The participant themselves will only benefit by having been able to share their experience about the Mosie Kit. While they might receive a discount code towards the purchase of a future Mosie Kit, this is not considered a benefit but a thank you for participation. Note the discount code will be a standard code used for other marketing purposes in order to ensure there is no way for Mosie staff to know if the participant obtained it for completing the survey or obtained it via other marketing avenues. The participant may feel good because they shared their experience and provided input into the Mosie Kit which will in turn help others.

The information obtained through this study will allow Mosie Baby to enhance or clarify the instructions provided with the Mosie Kit and will be considered in future production of the Mosie Kit.

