5.1 Inclusion Criteria

In order to be included in the study, the following inclusion criteria will be used.

Inclusion Criteria:

- Provide implicit consent by filling out and submitting the survey.
- Used a Mosie Kit to conceive during at least one cycle.
- At least 18 years old.
- Has an active email on file (presumed or they would not have received an invitation to participate. This information will not be verified as there is a desire to keep the survey completely anonymous.)

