5.2 Exclusion Criteria

The following exclusion criteria will be used.

Never used a Mosie Kit

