6.3 Measures to Minimize Bias: Randomization and Blinding

This study will not have any masking or randomization. It is a retrospective study. Participant selection bias will be minimized by including all people who have purchased a Mosie Kit in the prior 2-8 whole months.

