9.3 Populations for Analyses

The population to be analyzed include any one using the Mosie Kit in the full 2-8 months prior to study commencement. Respondents can be male or female. Overall the data will be analyzed as a whole and stratified by sex (having ovaries and a uterus as indication of being a female), age and type of relationship.

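### The purchase-window frame mixes first-time users with earlier starters who failed and bought again, and no planned analysis separates them; section 9.3 also leaves out some of the people the plan invites

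*Combined protocol and SAP*

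**What the plan says.** The invitation frame is defined by purchase. Section 5 reads: "The study population will consist of all individuals who have purchased the Mosie Kit in the past 2-8 complete months prior to study initiation". The schema in section 1.2 adds, for this step, "No other inclusion/exclusion criteria applies at this point". Neither asks for a first purchase.

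Eligibility is defined by use, without a date. Section 5.1 requires "Used a Mosie Kit to conceive during at least one cycle", and the only exclusion in section 5.2 is "Never used a Mosie Kit".

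The analysis population is defined by use within a period. Section 9.3 reads: "The population to be analyzed include any one using the Mosie Kit in the full 2-8 months prior to study commencement".

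If recruitment is extended, section 5 says that "additional potential participants will be invited who have purchased the kit at least 2 full months prior to being invited". That lag runs from invitation, not from study commencement.

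On the product, section 2.3.2 says: "Each Mosie Kit provides syringes for two inseminations to occur within a cycle". The primary endpoint in section 3 is the pregnancy rate after up to 6 cycles.

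On bias, section 6.3 says: "Participant selection bias will be minimized by including all people who have purchased a Mosie Kit in the prior 2-8 whole months".

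**The concern.** If a kit serves one cycle, a user who fails has a reason to buy again and a user who conceives usually has not. Take two users who first used the kit 10 months before the study. One conceives in her first cycle, never orders again, and is not on the list. The other fails, reorders inside the window, is invited, meets 5.1, and can report her failed cycles from before the window. Failures from before the window are thus recorded while most of the matching successes are not. This is prevalent-user, or left-truncated, sampling on the outcome itself.

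Section 9 has no first-user restriction, no truncation adjustment and no sensitivity analysis for it, and section 6.3 asserts the opposite. Both primary hypotheses rest on these pregnancy rates. A larger sample narrows the interval but does not remove this error.

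The second issue is one of definition. Section 5 counts purchases and section 9.3 counts use, with different reference dates for extension invitees, so the denominator is not the same set of people that the plan recruits.

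**Working it through.** **The plan's own precision figure.** The half-width is 1.96 x sqrt(0.25/n). At n = 500 it is 4.38%, and at n = 384 it is 5.00%. Both agree with section 9.2. They do not depend on who is in the frame, so they give no protection here.

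**One cohort by hand.** Inputs: 10% pregnancy per cycle (low end of the 10-15% in section 2.2); assumed one kit = one cycle = one month, nobody stops after a failure, and at most 6 cycles. Take 100 users whose first cycle falls in the month before the window opens.
- Cycle 1: 10 conceive and do not reorder; 90 fail, reorder and are invited.
- Pregnancies among the 90 in cycles 2-6: 90 x (1 - 0.9^5) = 36.9.
- Cycles reported by the 90: 90 + 90 x (1 - 0.9^5)/0.1 = 458.6.
- Recorded per-cycle rate: 36.9/458.6 = 8.0%.
- All 100 would give (10 + 36.9)/(100 + 368.6) = 10.0%.

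**Whole frame, 6-cycle cap.** Simulation of 2,000,000 users with steady inflow over 26 months; the frame is any kit used 2-8 months back. True rate 10% per cycle:

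| Stopping after each failure | Earlier starters in frame | Pooled per-cycle rate | Per person, frame v in-window starters |
|---|---|---|---|
| 0% | 38% | 7.7% | 35.6% v 40.3% |
| 20% | 26% | 8.2% | 27.2% v 28.3% |
| 40% | 16% | 8.7% | 20.3% v 20.4% |

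The earlier starters' own recorded per-cycle rate is 5.0%. With a true 15%, the pooled rate is 11.7%, 12.4% and 13.2%.

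**Does the per-person direction hold?** A separate month-by-month enumeration used 60-100% continuation and caps of 6 or 12 cycles.
- Same rate for everyone (10% or 15%), 6-cycle cap: 0 to -3.3 points.
- Mixed fertility (half at 5% and half at 20%, or half at 2% and half at 23%), either cap: 0 to -5.4 points.
- Same rate for everyone, 12-cycle cap: +0.2 to +4.1 points (for example 42.8% in the frame v 39.6% for in-window starters at 10% with no stopping).

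The reversal comes from exposure. A carried-in user who started 9 months back and failed once may have had 8 further cycles by the survey, a chance of 1 - 0.9^8 = 57%. A first user from 2 months back has had two, a chance of 1 - 0.9^2 = 19%. The per-cycle rate fell in every scenario.

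**Section 9.3 against section 5.** Assume even purchases over the six months from 8 to 2 months back, and first use spread evenly over the month after purchase. One sixth of buyers purchase in the last month of the window and half of those first use the kit after the 2-month point: 1/6 x 1/2 = 1/12, about 8%. These people are invited but fall outside 9.3 as written. A buyer who becomes eligible only through an extension purchased less than 2 months before commencement, so any first use also falls outside it.

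**The case against.** The strongest reply is about the endpoint. The primary endpoint is per person, and section 9.1 compares total pregnancy rates with the literature; no per-cycle rate is planned for that test. A reader might infer that the frame lowers the primary rate. The documents do not support that. The per-person shift is negligible at 40% stopping and about 1 point at 20% under a 6-cycle cap, and it changes sign with a longer cap. The outcome question visible in Appendix A sets no cycle limit.

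A reader might also infer that users who conceived before the window never enter. That is too strong: one who reorders after a loss or for another child is invited. The extension clause also states no 8-month upper bound.

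Nor do sections 5, 5.1 and 9.3 amount to three rival definitions. They can be read in sequence as invitation list, eligibility screen and analysis set, and section 5 expects use within a month of purchase. Only the purchase/use and reference-date mismatch between 5 and 9.3 needs reconciling.

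The sizes rest on inputs the documents do not give: repeat-purchase share, continuation and monthly sales. One kit per cycle is itself an inference, because a kit holds two syringes and someone inseminating once per cycle could use it for two. Finally, several survey screens are not shown, so a date of first use may be collected.

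All of this stands as a limit on direction and size. None of it supplies a first-user analysis, and a collected date would not help unless section 9 used it.

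**Conclusion.** The concern holds in this form. The frame admits repeat buyers who failed before the window and under-represents those who succeeded before it, and the plan does not separate them. Any crude per-cycle rate from these data is biased downward, illustratively to 7.7-8.7% against a true 10%. The per-person primary rate is distorted by an amount the documents do not determine: from about 5 points down to about 4 points up, depending on stopping, the cycle cap and mixed fertility. The larger of these shifts match or exceed the planned 4.4-point margin. The section 6.3 statement that inviting all purchasers minimizes selection bias therefore does not hold.

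Separately, and without any model, 9.3 as written leaves out recent buyers invited under the extension, and it leaves out late-window buyers who first used the kit in the last 2 months (about 8% under even purchasing). The first part is a design weakness that should be addressed; the second is a drafting correction.

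**What to change.** - Keep 5.1 as the eligibility rule. Making first use in the window an eligibility condition would exclude earlier starters and prevent reporting on them.
- Replace 9.3 with: all respondents meeting 5.1, including those invited under an extension.
- Collect the month of first Mosie use, unless a screen not shown already does so. The survey is anonymous with no follow-up (section 4.3), so it cannot be recovered later; Appendix A already allows questions to be revised.
- Run both primary hypotheses on respondents whose first use falls on or after the start of the 8-month window. Report all respondents, and earlier starters, separately.
- Pre-specify that, if the first-user set falls below 384, its result is a sensitivity analysis shown beside the all-respondent result.
- Remove or qualify the selection-bias statement in 6.3.

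The cost is one survey item, some rewording and a smaller primary set. Of the 600 responses expected in section 9.2, a 26% earlier-starter share leaves 600 x 0.74 = 444 (margin about 4.65%), below the target of 500. A 38% share leaves 600 x 0.62 = 372 (margin about 5.1%), below the minimum of 384. This does not equalise follow-up among in-window starters, so number of cycles attempted should be reported beside the rate.

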5.1 Inclusion Criteria

In order to be included in the study, the following inclusion criteria will be used.

Inclusion Criteria:

- Provide implicit consent by filling out and submitting the survey.
- Used a Mosie Kit to conceive during at least one cycle.
- At least 18 years old.
- Has an active email on file (presumed or they would not have received an invitation to participate. This information will not be verified as there is a desire to keep the survey completely anonymous.)

5.2 Exclusion Criteria

The following exclusion criteria will be used.

Never used a Mosie Kit

5.3 Lifestyle Considerations

There are no exclusions due to lifestyle considerations as this is a one time cross-sectional survey of past experiences.

5.4 Screen Failures

Participants who are consented to participate in the study, and who do not meet one or more criteria required for participation in the trial during the screening procedures, are considered screen failures. If an individual identifies their age as less than 18 years old or as not having used the Mosie Kit which will be the first 2 questions, then the survey will automatically end. These participants will be designated as screen failures. Screen failures will not be rescreened or included in the study in the future as this study is expected to have a very short duration (approximately 30 days).

5.5 Strategies for Recruitment and Retention

Recruitment of participants will be conducted via a direct email campaign. Participants will receive multiple emails requesting their participation in the study. Specifically they will receive emails according to the following schedule:

	Email Content	Expected Date
Initial Email	Initial Invitation to participate	Day 0
Second Email	Reminder of invitation to participate	Day 7
Third Email	Reminder of invitation to participate	Day14
Fourth Email	Last week to participate survey	Day 21
Fifth Email	Final email - 2 days left to complete survey	Day 28

If the study duration is expanded, a weekly email and a reminder a couple of days prior to the new deadline will be sent.

Typical response rates vary between 5-30% for email surveys. The rate of response is higher when people have a connection with the company or product. They also go up with repeated reminders and incentives to participate. A good survey response rate is about 50%.

Participants who complete the survey will receive a code to purchase a future Mosie Kit at a discount. This discount code will also be a code used in other marketing efforts in order to help reduce the likelihood a participant's status of participating in the study will remain masked.

The expected response rate for this study is between 30-50%. This response rate is expected because the potential participants will have all previously purchased a Mosie Kit. Additionally, the Mosie Newsletter has about a 20% open rate so it is expected that participation might be slightly higher than this.

Because participants will only be selected from people who have previously purchased a Mosie Kit there will be a limit in the mix of people available for selection for study participation. This means the results might not be generalizable to the public in general, nonetheless it is a representative sample of the people who would do at-home insemination.

6 STUDY INTERVENTION(S) OR EXPERIMENTAL MANIPULATION(S)

6.1 Study Intervention(s) or Experimental Manipulation(s) Administration

6.1.1 Study Intervention or Experimental Manipulation Description

This is a cross-sectional retrospective observational study of people who have selected to voluntarily purchase and use the Mosie Baby at-home insemination kit. No additional intervention or manipulation is planned for this study.

6.1.2 Administration and/or Dosing

This study retrospectively examines the administration and dosing of semen during insemination in the home environment by using the Mosie Kit. The recommended dosing of semen to produce a positive pregnancy outcome is at least 2 times in a cycle. With the first dose preferably administered within 24 hours of the first signs of ovulation and the second one between 24-48 hours post ovulation confirmation. Since this study is retrospective, it will not influence dosing, but merely will collect information on the dosing frequency and timing.

